### **8.8.3 Clinical Laboratory Evaluations**

Summary statistics for each scheduled time point measured and mean changes from baseline to each time point (when applicable) will be presented for clinical laboratory results.

All laboratory evaluation summaries will include the patients in the Double-blind Safety Population who have at least 1 postbaseline time point (for criteria based on postbaseline

assessments) and with both a baseline and at least 1 postbaseline time point (for criteria evaluating changes from baseline).

Laboratory values will be reported in Système International units.

Laboratory test results will be assigned an L/N/H classification according to whether the value was below (L), within (N), or above (H) the laboratory parameter's reference range. Comparisons will be based on 3×3 tables (shift tables) that, for a particular laboratory test, compare the baseline L/N/H classification to the highest and/or lowest L/N/H classification during the treatment period. Clinically important laboratory values based on prespecified criteria defined in the SAP will also be summarized.

Additionally, alanine aminotransferase, aspartate aminotransferase, bilirubin, and alkaline phosphatase will be presented in a separate listing, with 3× and 5×ULN flagged for alanine aminotransferase and aspartate aminotransferase; 2×ULN flagged for bilirubin, and 1.5×ULN flagged for alkaline phosphatase.

#### **8.8.4 Vital Signs and ECGs**

Summary tables will include descriptive statistics for baseline and each postbaseline assessment. Descriptive statistics will be calculated on both the actual score and the change from baseline score. Baseline is defined as the last measurement taken on or prior to the first day of dosing. Note that the Day 1 assessment can be included in the evaluation of baseline if that the assessment is performed prior to dosing.

All vital sign summaries will include the patients in the Double-blind Safety Population who have at least a postbaseline time point (for criteria based on postbaseline assessments) and with both a baseline and at least 1 postbaseline time point (for criteria evaluating changes from baseline).

Clinically notable vital signs will be identified based on the criteria defined in the SAP. For each vital sign parameter, the number and percentage of patients with at least 1 notable value will be tabulated by week and overall for the Double-blind Phase.

All vital signs will be listed in by-patient listings, including visit and collection date/time, and will be sorted by patient identifier and date/time of assessment.

Electrocardiogram results include an overall interpretation of 'normal,' 'abnormal but not clinically significant,' or 'abnormal and clinically significant.' These results will be tabulated at each time point.

Electrocardiogram results will be listed for each visit, including visit, whether ECG was performed (yes/no), explanation (if not performed), assessment date/time, study date, overall interpretation, and relevant medical history number or adverse event number, if deemed a clinically significant abnormality.

## **8.9 Additional Analyses**

### **8.9.1 Inflammatory Biomarkers**

The observed value and the change in inflammatory biomarkers (eg, IL-6, IL-8, and granulocyte macrophage-colony stimulating factor) from pre-dose to the end of the Double-blind Treatment Period (Week 12) will be presented by treatment group. Univariate and multivariate analyses of the change in inflammatory biomarkers will be described in an analysis plan, separate from the study SAP.

### **8.9.2 Missed Dialysis Visits and Incidence of Infection**

The number and percentage of patients who missed 1 or more dialysis visits during the Double-blind Treatment Period, and the total number of missed dialyses visits will be tabulated overall and by treatment group.

Incidence of infections based on adverse events, hospitalizations, and/or use of antibiotics for treatment of infection related to uremic pruritus will be analyzed using Fisher's Exact Test.

---

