### **6.3 Removal of Patients from Therapy or Assessment**

#### **6.3.1 Discontinuation of Individual Patients**

A patient may withdraw from the study at any time at his/her own request for any reason without prejudice to future medical care by the physician or at the institution.

A patient may be withdrawn at any time due to the following reasons:

1. At the discretion of the Investigator or the Sponsor for safety, behavioral, compliance, or administrative reasons, including, but not limited to:
  - a. Lost to follow-up;
  - b. Adverse event;
  - c. Lack of therapeutic efficacy;
  - d. Pregnancy;
  - e. Eligibility (Inclusion/exclusion criteria);
  - f. Subject non-compliance;
  - g. Subject withdrew consent.
2. If a patient misses 3 consecutive doses either on Week 11 or Week 12 of the Double-blind Treatment Period (these patients may still be eligible for the Open-label Extension Phase at the discretion of the Investigator in consultation with the Sponsor).
3. If patient misses 6 consecutive doses at any time during the Double-blind Treatment Period (these patients may still be eligible for the Open-label Extension Phase at the discretion of the Investigator in consultation with the Sponsor).
4. At the discretion of the Sponsor/Medical Monitor, if a patient receives a prohibited concomitant medication according to [Table 1](#).

- 
5. Any patient who becomes pregnant during treatment must be withdrawn from the study (see [Section 6.5.4.7](#)).

Whenever possible, withdrawal of a patient from study drug by the Investigator should be discussed with the Medical Monitor before the patient stops study drug.

If study drug is discontinued, regardless of the reason, an Early Termination Visit should be completed at the first dialysis after the last dose of study drug or, if not feasible during that timeframe, as soon as feasible. If at all possible, a Follow-up Visit is to be completed 7-10 days after the Early Termination Visit.

A patient may withdraw consent from continued participation in the study at any time. Although a patient will not be obliged to give a reason for withdrawing prematurely, the Investigator must make a reasonable effort to obtain the reason while fully respecting the patient's rights. The reason(s) for termination and date of stopping study drug must be recorded on the electronic case report form (eCRF) and source documents.

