### 8.8.1 Exposure to Study Drug

For this study, the duration of double-blind treatment for each individual patient may be up to 12 weeks, for a total of approximately 36 doses of study drug administered immediately following each dialysis session. Day 1 of the Double-blind Treatment Period will be defined as the day of administration of the first dose of study drug. The last day of the Double-blind Treatment Period will be defined as the day of the dialysis session immediately following the last injection of study drug.

Exposure and treatment compliance during the Double-blind Treatment Period will be summarized by the following parameters:

- Duration of treatment (days)
- Total number of doses actually received
- Number of missed doses

Duration of treatment (days) = (date of first dialysis after last dose) – (date of first dose) + 1.

If a patient receives additional dialysis during a given week for any reason, an additional dose of CR845 will be administered following dialysis. A maximum of 4 doses per week is allowed. No additional doses will be given for patients receiving an additional unscheduled ultrafiltration treatment. The number of patients getting such an extra treatment will be summarized.

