### 8.8.2 Adverse Events

All adverse events, as reported by the site, will be coded using MedDRA to MedDRA SOC and Preferred Term for standardization and summary purposes.

All reported adverse events (whether or not treatment-emergent) will be included in a by-patient adverse event listing. Only TEAEs will be included in summary tables which will present results by treatment group and by study period, as appropriate.

Adverse events that are considered “treatment emergent” relative to the Run-in Period are identified as any adverse event with an onset date after the start of the Run-in Period and up to the first dose of study drug during the Double-blind Period.

Adverse events that are considered “treatment emergent” relative to the Double-blind Period are identified as any adverse event

- with an onset date after the first dose of the double-blind study drug up to the Follow-up Visit or Early Termination Visit (or 7 to 10 days after the last dose if no Early Termination Visit was conducted), whichever is later, for patients who do not enter the Open-label Extension Phase.

- with an onset date after the first dose of the double-blind study drug up to the first dose of open-label drug for patient who continue into the Open-label Extension Phase.

The number and percentage of patients experiencing TEAEs will be summarized by treatment group and by period. A patient will be counted only once in the incidence count for a MedDRA SOC or Preferred Term, although a patient may have multiple occurrences (start and stop) of an event associated with a specific MedDRA Preferred Term or SOC. The most frequent TEAEs ( $\geq 5\%$  of patients in any treatment group) will also be tabulated by SOC and Preferred Term.

The incidence and percentage of patients experiencing treatment-emergent SAEs and TEAEs leading to study discontinuation will be presented by the appropriate MedDRA SOC and Preferred Term. Adverse events that result in death will also be summarized.

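### Section 8.9.2 summarises missed dialysis visits and infections without a denominator of scheduled visits or time at risk, so a dropout imbalance between arms would distort both modestly

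*Protocol*

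**What the plan says.** Protocol section 8.9.2 fixes three summaries for the double-blind period:

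- a crude proportion: "The number and percentage of patients who missed 1 or more dialysis visits during the Double-blind Treatment Period";
- a raw total: "the total number of missed dialyses visits will be tabulated overall and by treatment group";
- a test of infection incidence, identified from adverse events, hospitalizations or antibiotic use, where infection "related to uremic pruritus will be analyzed using Fisher's Exact Test".

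Other sections determine how long each patient is observed. Section 8.8.1 closes the period individually: its "last day of the Double-blind Treatment Period will be defined as the day of the dialysis session immediately following the last injection" of study drug. Under section 6.3.1, when study drug is stopped, "an Early Termination Visit should be completed at the first dialysis after the last dose of study drug" or as soon as feasible afterwards, with a follow-up visit 7 to 10 days later if possible. For patients who do not enter the extension, section 8.8.2 counts treatment-emergent events only up to those visits. A completer has up to 36 doses over 12 weeks (section 6.1.1.3). Patients who stop after the first dose are not replaced (section 6.3.1).

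**The concern.** A patient who stops at the end of Week 3 has about 9 scheduled sessions at which a miss can be counted, against 36 for a completer, and is also watched for infection over a shorter time. A total, a percentage of patients, or a two-by-two test treats both patients as equally observed. If one arm loses more patients for reasons unrelated to missed dialysis or infection, that arm shows fewer of both even when the underlying rates are the same.

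The infection result is the one most likely to be read as a finding. It carries a p-value, and section 4.1 presents fewer serious complications of itch, after naming infections among them, as part of the rationale for the drug. Missed visits are only tabulated, but a reader will still compare the two columns.

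**Working it through.** Section 8.9.2 states no figure to reproduce. The size therefore has to be illustrated under assumptions, because the protocol gives no dropout, missed-visit or infection rate for this trial.

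**Inputs from the protocol:** 175 patients per arm (section 8.2); 36 sessions over 12 weeks (section 6.1.1.3).

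**Assumptions:** equal true rates in both arms; dropout *d* unrelated to the outcome, 5% in one arm and 10%, 15% or 20% in the other; 5% of scheduled visits missed; a 12-week infection risk of 20% with a constant hazard.

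**Total missed visits.** With dropout spread evenly, a dropout is observed for half the period on average, so mean exposure is 1 − *d*/2. Expected total = 175 × 36 × 0.05 × (1 − *d*/2) = 315 × (1 − *d*/2). The assumed 5% cancels in the ratio.

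**Patients with at least one miss.** Assuming independent misses and dropouts leaving halfway, a completer's probability is 1 − 0.95^36 = 0.842 and a dropout's is 1 − 0.95^18 = 0.603. The proportion is (1 − *d*) × 0.842 + *d* × 0.603.

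**Crude infection risk.** Hazard over the period λ = −ln(0.8) = 0.223. The average risk of a dropout leaving at a uniformly distributed time is 1 − 0.2/λ = 0.104. Crude risk = (1 − *d*) × 0.20 + *d* × 0.104.

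| Dropout | Total missed visits | Ratio | At least one miss | Ratio | Crude infection risk | Ratio |
|---|---|---|---|---|---|---|
| 10% vs 5% | 299 vs 307 | 0.974 | 81.8% vs 83.0% | 0.986 | 19.0% vs 19.5% | 0.975 |
| 15% vs 5% | 291 vs 307 | 0.949 | 80.6% vs 83.0% | 0.971 | 18.6% vs 19.5% | 0.951 |
| 20% vs 5% | 284 vs 307 | 0.923 | 79.4% vs 83.0% | 0.957 | 18.1% vs 19.5% | 0.926 |

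With 5% dropout in both arms every ratio is 1.

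**Earlier dropout.** If all dropout falls at Week 3, the infection risk ratios become 0.962, 0.924 and 0.887.

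**Effect on the test.** In the evenly spread case, at 20% infection risk, Fisher's test rejects in favour of the arm with more dropout with probability 1.8% when dropout is equal, and 2.4%, 3.1% and 4.0% in the three rows.

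**A truly worse arm.** A true rate ratio of 1.25 in an arm with 15% versus 5% dropout still gives crude risks of 22.6% versus 19.5%, so that arm looks worse, as it should.

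**What a denominator does.** At 20% versus 5% dropout, scheduled visits on treatment are 175 × 36 × 0.90 = 5,670 and 175 × 36 × 0.975 = 6,142.5. Then 283.5/5,670 and 307.1/6,142.5 are both 5.0 per 100, which recovers the equality that was assumed.

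**The case against.** The best reply is that this is detail for the SAP, which section 8.1 gives primacy over the protocol for double-blind analyses. These are additional analyses outside the objectives and the testing sequence of section 8.7.3. Section 8.8.1 already summarises treatment duration, doses received and missed doses, so exposure will be visible. Crude incidence also matches the adverse event tables in section 8.8.2. The low priority that follows from this stands. The SAP argument does not remove the point, because section 8.9.2 states these summaries and the test outright.

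Three stronger readings are tempting, and the documents do not support them.

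- A reader might infer that the arm with more dropout looks better by construction. That needs unequal dropout largely unrelated to the outcome. Patients who stop after a first event still count in the proportions, and a truly worse arm can still look worse.
- A reader might infer that CR845 will be the arm flattered, from the Phase 2 treatment-emergent SAE figures in section 4.2.2 (21% versus 9%). Those pool three doses and are not discontinuations. Section 6.3.1 also lists lack of efficacy as a withdrawal reason, which could raise dropout on placebo instead.
- A reader might infer that counting stops in exactly the patients who miss most, since section 6.3.1 provides for withdrawal in these words: "If patient misses 6 consecutive doses at any time during the Double-blind Treatment Period". Withdrawal there is permissive. The companion rule on 3 consecutive doses applies only in Weeks 11 and 12. The qualifying misses precede withdrawal, and whether they are counted depends on whether section 8.8.1 means the next attended or the next scheduled session. A dose is also not the same thing as a dialysis visit.

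It is also fair that a rate does not cure outcome-dependent stopping. Misses per scheduled visit are affected by it too, and patient-time rates assume a roughly constant hazard.

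**Conclusion.** The point holds in a limited form. The three summaries ignore unequal observation time, and a dropout imbalance unrelated to the outcomes would pull both results down in the arm that loses more patients. At 10% to 20% versus 5% dropout the relative deficit is about 3% to 8% for total missed visits, 2% to 7% for crude infection risk, and 1% to 4% for the percentage with at least one miss. The larger figures for totals should not be carried over to that percentage.

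All of these rest on assumed rates, equal true rates and non-informative, evenly spread dropout. For infections they also treat observation as ending at dropout. Where adverse events are collected to a follow-up visit 7 to 10 days after early termination, the real effect is somewhat smaller. Only infections are formally tested, and the shift in that test's behaviour is slight. Nothing in the primary or secondary conclusions depends on this.

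**What to change.** In section 8.9.2, keep the crude figures and add the following by arm:

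- missed dialysis visits per 100 scheduled visits on double-blind treatment;
- first infections per patient-time at risk, with a 95% CI for the rate ratio.

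State that the rates assume a roughly constant hazard and stopping unrelated to the outcome. Say also whether the period in section 8.8.1 ends at the next attended or the next scheduled session, since that decides which misses are counted.

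The cost is a few sentences and minor programming. Section 8.8.1 already derives treatment duration and missed doses, dialysis follows a three-times-weekly schedule, and missed visits and adverse events are already recorded. No new data are needed.

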## **9.0 Quality Control and Quality Assurance**

### **9.1 Study Monitoring Plan**

Monitoring and auditing procedures that comply with current Good Clinical Practice (GCP) guidelines will be followed, including remote and onsite review of the eCRFs via an electronic data capture system for completeness and clarity, source document verification, evaluation of protocol adherence, appropriate documentation of informed consent procedures, safety reporting, study drug storage, and dispensation. The study will be monitored by the Sponsor or its designee (contract research organization). Monitoring will be performed by a representative of the Sponsor or its designee (site monitor) who will review patient enrollment, eCRFs, source documents, drug accountability records, and reporting and recording of adverse events. The site monitor will ensure that the investigation is conducted according to protocol design and regulatory requirements by frequent site visits and communications (letter, telephone, and facsimile).

The site monitor(s) will follow written standard operating procedures as agreed with the contract research organization and the Sponsor. The site monitor(s) will verify that the clinical study is conducted and data are generated, documented (recorded), and reported in compliance with the protocol, GCP, and the applicable regulatory requirements. Monitoring reports will be submitted to the Sponsor in a timely fashion as per details described in a clinical monitoring plan for this study.

Name and contact information for monitors will be included in the ISF.

### **9.2 Audits and Inspections**

The investigational site will maintain appropriate medical and research records for this study, in compliance with ICH-GCP, regulatory, and institutional requirements for the protection of confidentiality of participants. The Investigator must allow access to authorized persons or institutions to complete data source verification. Source data are all information, original records of clinical findings, observations, or other activities in a clinical study necessary for the reconstruction and evaluation of the study. Examples of these original documents and data records include, but are not limited to, hospital records, clinical and office charts, laboratory notes, memoranda, participants' diaries or evaluation checklists, pharmacy dispensing records, recorded data from automated instruments, copies or transcriptions certified after verification as being accurate and complete, microfiches, photographic negatives, microfilm or magnetic media, x-rays, and participant files and records kept at the pharmacy, laboratories, or medical-technical departments involved in the clinical study, as applicable.

The investigational site will provide access to all study-related sites, source data/documents, and reports for the purpose of monitoring and auditing by the Sponsor and inspection by local and regulatory authorities.

### **9.3 Data Collection, Validation, and Analysis**

A data management vendor will ensure that quality assurance procedures are implemented, beginning with the data entry system and generation of data quality control checks that will be run on the database.

---

## **10.0 Ethics and Regulatory Compliance**

### **10.1 Independent Ethics Committee or Institutional Review Board**

A properly constituted, valid IRB or IEC and the national regulatory authority, if required by the applicable laws in the country, must review and approve the protocol, the Investigator's Brochure, ICF, and related patient information and recruitment materials (if applicable) before the start of the study. It is the responsibility of the Investigator to ensure that written informed consent is obtained from the patient before any activity or procedure is undertaken that is not part of routine care.

The IRB/IEC will review all appropriate study documentation in order to safeguard the rights, safety, and well-being of the patients. The study will only be conducted at a site where IRB/IEC approval has been obtained.

If it is necessary to amend the protocol and/or ICF during the course of the study, the Investigator must ensure that the IRB/IEC and the national regulatory authority, if required by the applicable laws in the country, reviews and approves these amended documents. Except for changes necessary to eliminate an immediate hazard to study patients, or when the change involves only logistical or administrative aspects of the study (eg, change in monitor, change of telephone number), no amendments to the study protocol will be made without the prior written agreement of the Sponsor and acknowledgement by the Investigator and, as applicable, the IRB/IEC and the national regulatory authority, if required by the applicable laws in the country.

The Investigator(s) will maintain documentation of the composition of the IRB/IEC as well as all correspondence with the IRB/IEC. The Investigator(s) will comply with local requirements for routine reporting to the IRB/IEC as well as local and government requirements for notifying the IRB/IEC of SAEs. The Investigator will provide the Sponsor or its designee copies of all IRB/IEC approval notices, correspondence, annual reports, and final study progress reports.

### **10.2 Ethical Conduct of the Study**

The study will be conducted in accordance with the provisions of the Declaration of Helsinki (October 2013), FDA (CFR, Sections 312.50 and 312.56), EU (536/2014) and UK regulations (The Medicines for Human Use [Clinical Trials] Regulations 2004 [No.1031]), ICH GCP (CPMP 135/95), and with the applicable regulations of the countries in which the study is conducted.

The Investigator will be thoroughly familiar with the appropriate use of the study drug as described in the protocol, Investigator's Brochure, and any other study-related manual(s). Essential clinical documents will be maintained to demonstrate the validity of the study and the integrity of the data collected. A study master file must be established for the study, and retained according to the appropriate regulations.

---

